9.3.2 Regulatory Reporting for Studies Conducted Under DMID-Sponsored IND

Following notification from the site principal investigator or appropriate sub-investigator, DMID, the Investigational New Drug (IND) sponsor, will report any suspected adverse reaction that is both serious and unexpected. DMID will report an adverse event as a suspected adverse reaction only if there is evidence to suggest a causal relationship between the drug and the adverse event. DMID will notify FDA and all participating site principal investigators (i.e., all principal investigators to whom the sponsor is providing drug under its IND or under any principal investigator's IND) in an IND safety report of potential serious risks from clinical trials or any other source, as soon as possible, but in no case later than 15 calendar days after the sponsor determines that the information qualifies for reporting as specified in 21 CFR Part 312.32. DMID will also notify FDA of any unexpected fatal or life-threatening suspected

adverse reaction as soon as possible, but in no case later than 7 calendar days after the sponsor's initial receipt of the information. Relevant follow up information to an IND safety report will be submitted as soon as the information is available. Upon request from FDA, DMID will submit to FDA any additional data or information that the agency deems necessary, as soon as possible, but in no case later than 15 calendar days after receiving the request.

All serious events designated as "not related" to study product(s), will be reported to the FDA at least annually in a summary format.

9.3.3 Reporting of Pregnancy

Pregnancies occurring in study subjects will be reported via AdvantageEDCSM on the Pregnancy Report form. With the subject's permission, all protocol-required venous blood samples will be obtained, and the subject will continue to be followed for safety for the duration of this study. Efforts will be made to follow all pregnancies reported during the course of this study until approximately 1 to 2 months post-pregnancy pending the subject's permission.

9.4 Type and Duration of Follow-up of Subjects after Adverse Events

AEs will be collected, assessed, and followed through resolution from the time of study vaccination through approximately 28 days after study vaccination.

SAEs will be collected, assessed, and followed from the time of study vaccination through resolution even if this extends beyond the study-reporting period (approximately Day 181).

Resolution of an AE/SAE is defined as the return to pretreatment status or stabilization of the condition with the expectation that it will remain chronic.

If the site principal investigator or appropriate sub-investigator becomes aware of an acute febrile illness and the site principal investigator or appropriate sub-investigator decides to bring the subject in for an evaluation to determine etiology, then the site principal investigator or appropriate sub-investigator, at their own discretion, can determine the specific testing that should be performed.

Follow-up procedures, evaluations, and outcomes will be recorded on the appropriate data collection form.

9.5 Halting Rules

Further enrollment and study vaccinations will be halted for SMC review/recommendation if any of the following are reported:

- Any subject experiences ulceration, abscess, or necrosis in the nose that is considered related to study product administration, through the subject's last study visit.
- Any subject experiences laryngospasm, bronchospasm, or anaphylaxis within 1 day after administration of study product that is considered related to study product.
- Two or more subjects experience generalized urticaria within 3 days after administration of study product that is considered related to study product.
- Any subject experiences a study product-related SAE from the time of study vaccination through the subject's last study visit.
- Any subject experiences acute weakness of limbs and/or cranial nerve innervated muscles (description of potential signal of GBS) after administration of study product, through the subject's last study visit.

This study will also be halted for SMC review/recommendation if, within 8 days after administration of each study vaccination, any of the following occurs:

- Two or more subjects experience the same severe (Grade 3) mucosal Reactogenicity adverse event (table in [section 9.2.2](#)).
- Two or more subjects experience the same severe (Grade 3) Subjective Systemic Reactogenicity adverse event. Grading scales for solicited reactions are included in [Section 9.2.2](#).
- Two or more subjects experience the same severe (Grade 3) Quantitative Systemic Reactogenicity adverse event. Grading scales for solicited reactions are included in [Section 9.2.2](#).
- Two or more subjects experience the same severe (Grade 3) study related laboratory adverse event (HGLT in MedDRA coding)
- Two or more subjects experience the same severe (Grade 3) study related unsolicited systemic adverse event (HGLT in MedDRA coding)

DMID retains the authority to suspend additional enrollment and study interventions/ administration of study product during the entire study, as applicable.

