7.3.3 Visit 4, Day 29, Clinic Visit (Window: Day 29 ± 3 days)

- Interim medical history, including an assessment for new medical conditions, will be obtained by interview of subjects and any changes since the previous clinic visit or contact will be noted.
- All concomitant medications and vaccines will be recorded on the appropriate data collection form.
- All AE/SAEs will be recorded on the appropriate data collection form.
- A targeted physical examination may be performed, if indicated based on review of interim medical history, by a study clinician.
- Approximately 10 mL of venous blood will be collected for antibody assays.

-
- For subjects who consent to additional future use samples, approximately 24 mL of venous blood will be collected for PMBC isolation and possible future research.
 - Nasal samples will be obtained for *B. pertussis* culture and immunological assays. If culture is positive for *B. pertussis*, the isolate will be cryopreserved as detailed in the MOP.

7.3.4 Visit 4a (If needed, based on *B. pertussis* positive culture on Day 29), Day 46, Clinic Visit (Day 46 ± 3 days)

- Interim medical history, including an assessment for new medical conditions, will be obtained by interview of subjects and any changes since the previous clinic visit or contact will be noted.
- All concomitant vaccines will be recorded on the appropriate data collection form.
- All SAEs will be recorded on the appropriate data collection form.
- A targeted physical examination may be performed, if indicated based on review of interim medical history, by a study clinician.
- Nasal samples will be obtained for *B. pertussis* culture (if necessary-positive from day 29) and immunological assays. If culture is positive for *B. pertussis*, the isolate will be cryopreserved as detailed in the MOP.

7.3.5 Visit 4b (if needed, based on positive *B. pertussis* culture from Day 46), Day 50, Phone Call (Day 50 ± 3 days)

- If a participant's sample from Visit 4a is positive for *B. pertussis*, a study investigator will prescribe a 5-day course of azithromycin (500 mg orally once per day).

7.4 Final Study Visit, Visit 5, Day 181, Clinic Visit (Day 181 ± 21 days)

- Interim medical history, including an assessment for new medical conditions, will be obtained by interview of subjects and any changes since the previous clinic visit or contact will be noted.
- All concomitant vaccines will be recorded on the appropriate data collection form.

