7.5 Early Termination Visit

The following activities will be performed at the early termination visit for subjects who withdraw or are withdrawn/terminated from this study:

- Interim medical history, including an assessment for new medical conditions, will be obtained by interview of subjects and any changes since the previous clinic visit or contact will be noted.
- Memory aid information will be reviewed with subjects (if within 15 days after study vaccination).
- All concomitant medications will be recorded on the appropriate data collection form (if prior to 29 days after study vaccination).
- All non-study vaccines will be recorded on the appropriate data collection form (if prior to 181 days after study vaccination).
- All AE/SAEs will be recorded on the appropriate data collection form. Only SAEs will be recorded after 28 days following study vaccination.
- Vital signs, including oral temperature, pulse, and blood pressure, may be obtained if indicated based on clinical history. Subjects must not eat or drink anything hot or cold, or smoke within 10 minutes prior to taking oral temperature.
- A targeted physical examination may be performed, if indicated based on review of interim medical history, by a study clinician.
- Post-administration reactogenicity assessments will be performed (if within 15 days after study vaccination).

-
- Venous blood will only be obtained if the early termination visit occurs: 1) prior to Visit 2, 2) after day 14 post-vaccination but before Visit 3, or 3) at least 28 days following Visit 3.
 - Approximately 10 mL of venous blood will be collected for antibody assays.
 - For subjects who consent to additional future use samples, approximately 24 mL of venous blood will be collected for PBMC isolation and possible future research.

7.6 **Unscheduled Visit**

Unscheduled visits may occur at any time during this study. Any of the following activities may be performed:

- Interim medical history, including an assessment for new medical conditions, will be obtained by interview of subjects and any changes since the previous clinic visit or contact will be noted.
- Memory aid information will be reviewed with subjects (if within 15 days after study vaccination).
- All concomitant medications will be recorded on the appropriate data collection form (if prior to 29 days after study vaccination).
- All non-study vaccines will be recorded on the appropriate data collection form (if prior to 181 days after study vaccination).

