9.2.5 Adverse Events of Special Interest

Medically attended wheezing events will be considered adverse events of special interest given the route of study product administration and the nature of the study product (i.e., a live attenuated bacterial vaccine). Though subjects with a history of persistent asthma will be excluded from the study, it is possible that new onset wheezing episodes could occur. These will be evaluated by a study investigator and relatedness to study product will be assessed. Medically attended wheezing events will be evaluated through Day 29.

9.2.6 Procedures to be Followed in the Event of Abnormal Laboratory Test Values or Abnormal Clinical Findings

Solicited mucosal site and systemic reactogenicity events will be documented and reported from the time of study vaccination through 14 days (Day 15) after study vaccination.

Unsolicited, non-serious AEs will be documented from the time of study vaccination through approximately 28 days (Day 29) after study vaccination.

SAEs will be documented from the time of study vaccination through approximately 6 months post vaccination.

[figure not shown]
In addition, if a subject has an abnormal laboratory test value (e.g., complete blood count or serum chemistries), it will be recorded as an AE and will be graded per toxicity table and will be followed up until resolution.

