9.3 Reporting Procedures

9.3.1 Serious Adverse Events

SAEs will be followed until resolution even if this extends beyond the study-reporting period. Resolution of an AE is defined as the return to pretreatment status or stabilization of the condition with the expectation that it will remain chronic.

Any AE that meets a protocol-defined serious criterion must be submitted immediately (within 24 hours of site awareness) on an SAE form to the DMID Pharmacovigilance Group at the following address:

In addition to the SAE form, selected SAE data fields must also be entered into AdvantageEDCSM. Please see the protocol-specific MOP for details regarding this procedure.

Other supporting documentation of the event may be requested by the DMID Pharmacovigilance Group and should be provided as soon as possible.

The site will send a copy of the SAE report(s) to the ISM when they are provided to the DMID Pharmacovigilance Group. The DMID Medical Monitor and DMID Clinical Project Manager will be notified of the SAE by the DMID Pharmacovigilance Group. The DMID Medical Monitor will review and assess the SAE for regulatory reporting and potential impact on study subject safety and protocol conduct.

At any time after completion of this study, if the site principal investigator or appropriate sub-investigator becomes aware of an SAE that is suspected to be related to study product, the site principal investigator or appropriate sub-investigator will report the event to the DMID Pharmacovigilance Group.

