The SMC will review grouped and unblinded data in the closed session only. The SMC will meet and review this data at scheduled time points or ad hoc as needed during this study as defined in the SMC charter. As an outcome of each review/meeting, the SMC will make a recommendation as to the advisability of proceeding with study vaccinations (as applicable), and to continue, modify, or terminate this study.

DMID or the SMC chair may convene the SMC on an ad hoc basis according to protocol criteria or if there are immediate concerns regarding observations during the course of the study. The DMID Medical Monitor is empowered to stop enrollment and study vaccinations if adverse events that meet the halting criteria are reported. The DMID Medical Monitor and the ISM will be responsible for reviewing SAEs in real time. The SMC will review SAEs on a regular basis and ad hoc during the study.

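### Two halting rules run to the last visit with no seriousness condition, but non-serious events need not be recorded after about Day 28

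*Protocol*

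**What the plan says.** **Halting rules.** Three single-subject rules in Protocol Section 9.5 run to the subject's last visit. One covers product-related SAEs. The other two carry no seriousness condition: a product-related nasal lesion ("ulceration, abscess, or necrosis in the nose that is considered related to study product administration, through the" subject's last visit), and acute limb or cranial-nerve weakness, which the rule describes as a possible sign of Guillain-Barré syndrome (GBS). The remaining rules in 9.5 close within 8 days of vaccination or sooner.

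**How a halt starts.** It depends on a report. The lead-in to 9.5 says "Further enrollment and study vaccinations will be halted for SMC review/recommendation if any of the following are reported", and Section 9.6.2 says "The DMID Medical Monitor is empowered to stop enrollment and study vaccinations if adverse events that meet the halting criteria are reported".

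**What is recorded, and until when.**
- Section 9.2.6: "Unsolicited, non-serious AEs will be documented from the time of study vaccination through approximately 28 days (Day 29) after study vaccination".
- Section 9.4: "AEs will be collected, assessed, and followed through resolution from the time of study vaccination through approximately 28 days after study vaccination".
- Sections 7.5 and 7.6 (early termination and unscheduled visits): "Only SAEs will be recorded after 28 days following study vaccination".
- Sections 7.3.4 and 7.4 (Visits 4a and 5): "All SAEs will be recorded on the appropriate data collection form".
- The ** footnote in Appendix A, repeated under SAP Table 1, confines assessment after 28 days to SAEs, NOCMCs and AESIs.

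**Timed reporting.** Section 9.3.1: "Any AE that meets a protocol-defined serious criterion must be submitted immediately (within 24 hours of site awareness) on an SAE form". No other event type has a stated deadline for reporting by the site.

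**The concern.** The related-SAE rule is fed by SAE collection, which runs to about six months. The other two long-running rules have no matching feed once non-serious recording stops. If the plan is followed as written, a product-related nasal ulcer that heals, or a transient weakness that is neither serious nor labeled GBS, could occur after Day 28 and satisfy 9.5 without entering the safety record. The SMC review that 9.5 calls for might then not start while others are still being vaccinated. After enrollment closes no vaccination is left to halt, and the effect is on the completeness of what the SMC sees at its final review.

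**Working it through.** The documents state no operating characteristic for the halting rules, so there is no plan figure to reproduce. The check compares windows and then asks how much vaccination would remain.

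**1. Length of the mismatch.** Non-serious recording ends at Day 29. Visit 5 is Day 181 ± 21 days.
- Nominal: 181 − 29 = 152 days.
- Over the visit window: 160 − 29 = 131 to 202 − 29 = 173 days.
- As a share of the nominal 180 days of rule coverage: 152/180 = 84%.

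This is calendar time, not risk. Section 2.1.2 reports that colonization in Phase 1b lasted through day 11–28.

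**2. What other text catches after Day 28.**

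| Route | What it catches | What it leaves |
|---|---|---|
| SAE definition (9.2.3) | GBS by name; important medical events by judgment | A case judged non-serious and not called GBS |
| NOCMC (9.2.4; primary outcome to Day 181 in 3.2.1) | New conditions that need continuing care | Self-limiting cases |
| AESI (9.2.5) | Medically attended wheezing | Nasal lesions and weakness |
| Subject's call to the site (7.2) | Severe reactions | Milder cases; no onward duty on the site |
| Interim history and targeted examination (7.3.4, 7.4; SAP 9.7, Listing 17) | May reveal a case at a visit | No duty to record it as an event |
| Monitoring against the halting rules (11.3.1) | A general commitment | No data source or timing named |

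Concomitant medications other than vaccines are also collected only to about 28 days (6.6), so treatment of a late lesion would not reveal it.

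**3. Vaccinations still to be given when a late case surfaces.** Enrollment is put at about 6 months in Section 5 and about 12 months in Section 4. Assume even accrual over E = 182 or 365 days. For an event surfacing d days after vaccination, a fraction f = max(0, 1 − d/E) of subjects reach that point before enrollment ends. Averaged over all 50 subjects, the share of vaccinations still to come is f²/2.

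| d (days) | f, E = 182 | Share | f, E = 365 | Share | Of 50 |
|---|---|---|---|---|---|
| 45 | 0.753 | 0.283 | 0.877 | 0.384 | 14–19 |
| 90 | 0.505 | 0.128 | 0.753 | 0.284 | 6–14 |
| 180 | 0.011 | 0.000 | 0.507 | 0.128 | 0–6 |

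**4. Who has a visit between Day 29 and Visit 5.** Only subjects who are culture-positive at Day 29 attend Visit 4a. The protocol gives no rate, saying only that most subjects in earlier studies had cleared by then. If 0% to 15% of the 15 + 15 + 5 = 35 vaccine recipients were positive (an assumption), attendance would be 0 to 0.15 × 35 = 5.3, so about 0 to 5 subjects. For everyone else, a late case before Visit 5 would surface only through an unscheduled or early termination visit, or contact by the subject.

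**The case against.** The best counter-argument is that the plan has more routes than AE forms, and that two relevant documents are not to hand. Section 9.6.2 allows ad hoc SMC meetings on immediate concerns and leaves SMC procedures to a charter. The independent safety monitor may look at other AEs and has access to records (9.6.1). DMID can suspend vaccination at any time (9.5). Interim history is mandatory at Visits 4a and 5. All of this stands, and the charter or MOP may contain a reporting route. But each visible route presupposes that the case has reached someone, and none requires a self-limiting, non-serious case to be recorded.

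A second argument also has force. The SAE-only wording in 7.5 and 7.6 cannot be literal, since it would exclude NOCMCs, a primary outcome to Day 181. It is better read as shorthand, so the case rests mainly on 9.2.6, 9.4 and the Appendix A footnote.

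Third, the residual case is small. A nasal lesion would have to arise after Day 28, be product-related, and be neither serious nor chronic. Weakness would have to escape the GBS, important-medical-event and NOCMC routes. That is correct, and it limits the weight of the point.

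A reader might infer that the missing reporting deadline is a consequence of the Day 28 cut-off. It is not: the 24-hour duty covers SAEs only throughout the trial, so a non-serious nasal ulcer on Day 10 has no deadline either.

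**Conclusion.** The mismatch is real but narrow. Two single-subject rules outlast the recording that would feed them by about 152 days (131–173), and no supplied document requires a non-serious, self-limiting case in that period to be recorded. Separately, no non-serious halting event has a timed reporting duty at any time point.

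A reader might go further and conclude that the two rules are inoperative for 84% of follow-up, or that late GBS or other serious events could be missed. The documents do not support that. SAEs, GBS and NOCMCs are captured throughout follow-up, sites may report other cases voluntarily, and the 84% measures calendar time rather than risk. Nor should the size be taken from an event at 28 days after vaccination: that is Day 29, still inside the collection window.

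The practical stake is the 28–38%, 13–28% and 0–13% of vaccinations remaining at 45, 90 and 180 days. These rest on even accrual and on the two stated enrollment periods, and they say nothing about how likely such an event is. The point is a low-cost improvement worth considering. Confidence is medium, because the MOP and SMC charter were not available.

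**What to change.** Record the two event types (nasal ulceration, abscess or necrosis; acute limb or cranial-nerve weakness) through the last visit regardless of seriousness. Require any event that may meet a 9.5 criterion, at any time point, to be reported promptly for the halting check, for example within 24 hours of site awareness.

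Places to change:
- Protocol 9.1, 9.2.6, 9.4 and 15.4.
- The Visit 4a, Visit 5, early termination and unscheduled visit lists.
- The Appendix A footnote and Visit 4a table.
- SAP 4.5.1, 9.3.2 and Tables 1 and 2.

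List these late events separately, so that the 28-day AE summaries keep their defined window.

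The cost is a small amendment with IRB approval and a few more non-serious events to record. There are no new visits or procedures, and the halting criteria do not change. The amendment does not shorten the contact gap between Day 29 and Day 181.

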7.3 Follow-up Visits

7.3.1 Visit 2, Day 8, Clinic Visit (Window: Day 8 ± 2 days)

- Interim medical history, including an assessment for new medical conditions, will be obtained by interview of subjects and any changes since the previous clinic visit or contact will be noted.
- Memory aid information will be reviewed with subjects.
- All concomitant medications and vaccines will be recorded on the appropriate data collection form.
- All AE/SAEs will be recorded on the appropriate data collection form.
- A limited physical examination will be performed, focused on the nasopharynx, oropharynx, and lungs; in addition, a targeted physical examination will be performed, if indicated, based on review of interim medical history, by a study clinician.

-
- Approximately 10 mL of venous blood will be collected for safety laboratory studies, to include a complete blood count (white blood cell count, platelet count, hemoglobin concentration) and serum chemistries (ALT and creatinine)
 - For subjects who consent to additional future use samples, approximately 24 mL of venous blood will be collected for PBMC isolation and possible future research.

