& Inclusive of reactogenicity assessments performed on the day of study vaccination through 14 days after study vaccination.

** Assessment of AE/SAE limited to new-onset chronic medical conditions, AESI, and SAEs if after 28 days following the study vaccination.

- ² To be performed locally by the site, and will include white blood cell count, hemoglobin, platelet count, alanine aminotransferase, serum creatinine, and HIV screening
- ^Ω Venous blood will only be obtained if the early termination visit occurs: 1) prior to Visit 2, 2) after day 14 post-vaccination but before Visit 3, or 3) at least 28 days following Visit 3.
- * See Schedule of Events secondary table for Visits 4a and 4b.

| Study Visit Number | V4a* | V4b** (Phone call) |
|--|--------|-----------------------|
| Study Day post study vaccination | D46±3d | Day 50 ± 3 days |
| Nasal Sample Collection for B. pertussis Culture and immunological assays | X | |
| Prescription of Azithromycin 500 mg by mouth once daily | | X |
| Interim Medical History | X | |
| SAE Assessment | X | |
| Targeted Physical Examination, if indicated | X | |
| Concomitant Non-study Vaccines | X | |

*Study visit only if nasal sample is positive for *B. pertussis* at Day 29

**Study visit only if nasal sample is positive for *B. pertussis* at Day 46

Venipuncture Volumes (mL)

| Study Visit Number | V00 | V01 | V02 | V03 | V04 | V05 | Early Termination (if needed) | Unscheduled (if needed) |
|--|-------------------------|-----------------------------|-----------|-----------|-----------|-----------|-------------------------------|-------------------------|
| Study Day post study vaccination | Screening (D-30 to D-1) | Enrollment and Dose 1 D1 | D8±2d | D15±3d | D29±3d | D181±21d | | |
| Venous Blood Collection for Screening Laboratory Assays ² | 10 | 0 | 0 | 0 | 0 | 0 | 0 | 0 |
| Venous Blood Collection for Safety Laboratory Assays | 0 | 0 | 10 | 0 | 0 | 0 | 0 | 0 |
| Venous Blood Collection for Serum Antibody Assays ³ | 5 | 10 | 0 | 10 | 10 | 10 | 10 | 0 |
| Venous Blood Collection for PBMC isolation and Future Research | 0 | 24 | 24 | 0 | 24 | 24 | 24 | 0 |
| Maximum Total* | 15 | 34 | 34 | 10 | 34 | 34 | 34 | 0 |

*Maximum total for up to 6 study visits (161 mL).

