9.6. Clinical Laboratory Evaluations

Clinical safety laboratory adverse events will be collected at the time of study vaccination through approximately 7 days after study vaccination (Day 8). Any clinical laboratory parameter that is abnormal at Day 8 will be repeated at the next study visit (or sooner if medically indicated) and followed until normal or stabilization. Parameters to be evaluated include white blood cell count, platelet count, hemoglobin concentration, alanine aminotransferase (ALT), and creatinine. Grading scales for safety laboratory parameters are presented in [Table 9](#).

The number and percentage of subjects with at least one clinical safety laboratory abnormality through Day 8 is presented in the overall summary of adverse events ([Table 34](#).)

The distribution of chemistry results by severity, time point, and treatment group will be presented in [Table 61](#), [Table 62](#), [Table 63](#), [Table 64](#), [Table 65](#), [Table 66](#), and [Figure 14](#). The distribution of hematology results by severity, time point, and treatment group will be presented in [Table 69](#), [Table 70](#), [Table 71](#), [Table 72](#), [Table 73](#), [Table 74](#), [Table 75](#), [Table 76](#), and [Figure 15](#). Descriptive statistics including mean, standard deviation, median, minimum and maximum values by time point, for each laboratory parameter, will be summarized in [Table 67](#) and [Table 68](#) (chemistry) and [Table 77](#), [Table 78](#), and [Table 79](#) (hematology). Changes in laboratory values will be presented in [Figure 16](#), [Figure 17](#), [Figure 18](#), [Figure 19](#), and [Figure 20](#).

Subject visits with abnormal laboratory results, Grade 1 severity or higher, will be presented in [Table 59](#) and [Table 60](#).

[Listing 14](#) and [Listing 15](#) will provide complete listings of individual clinical laboratory results with applicable reference ranges.

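### The laboratory halting criterion closes on Day 9, but the only scheduled safety sample that feeds it may be drawn on time on Day 10

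*Protocol*

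**What the plan says.** Protocol 9.5 has two lists of halting rules. The second applies if "within 8 days after administration of each study vaccination, any of the following occurs", and one of its entries is "Two or more subjects experience the same severe (Grade 3) study related laboratory adverse event", with sameness judged at a MedDRA grouping level.

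Protocol 7.3.1 sets Visit 2 as "Clinic Visit (Window: Day 8 ± 2 days", and there "Approximately 10 mL of venous blood will be collected for safety laboratory studies": blood count, ALT and creatinine. In the Appendix A schedule, the row "Venous Blood Collection for Safety Laboratory Assays" is marked at Visit 2 only, and the venipuncture table gives 10 mL at that visit and 0 at every other.

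On day numbering, Protocol 7.2 makes vaccination Day 1. Protocol 9.2.6 collects solicited events "through 14 days (Day 15) after study vaccination". SAP 9.6 equates 7 days after vaccination with Day 8 for these same laboratory tests, and has abnormal Day 8 values repeated at the next visit, or sooner if medically indicated.

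**The concern.** A halting rule should be able to use every on-time result from the assessment that feeds it. Here the rule closes one day before the sampling window does. Two subjects with the same related Grade 3 ALT rise, both sampled on schedule, could trigger a halt or not depending only on whether one appointment fell on Day 9 or Day 10.

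This is a live bacterial vaccine, and part of the oversight is keyed to the same criteria. Protocol 9.6.2 says "The DMID Medical Monitor is empowered to stop enrollment and study vaccinations if adverse events that meet the halting criteria are reported". That section also lists a single scheduled SMC data review before the final one, after the first 25 subjects. For the remaining 25 or so the pre-set trigger may carry more of the load, although the SMC charter, which is not among the documents, may add reviews.

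**Working it through.** **Day numbering.** The rule study day = 1 + days after vaccination reproduces the pairs the documents state: 7 days and Day 8 (SAP 9.6), 14 and Day 15, 28 and Day 29 (Protocol 9.2.6), and 45 and Day 46 (Protocol 11.4).

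**Limit against window.** The halting limit is 8 days after vaccination, so 1 + 8 = Day 9. Visit 2 is on time from 8 − 2 = Day 6 to 8 + 2 = Day 10.

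| Visit 2 drawn on | Days after vaccination | Within 8 days? |
|---|---|---|
| Day 6 | 5 | yes |
| Day 7 | 6 | yes |
| Day 8 | 7 | yes |
| Day 9 | 8 | yes |
| Day 10 | 9 | no |

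If vaccination were instead counted as Day 0, Day 9 would also fall outside, so neither convention closes the gap.

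**Could other text bring the value in?** Nothing ties the criterion to the Visit 2 sample or its window. A repeat after a Day 10 draw is later still. The rules in 9.5 that run to the last visit cover related SAEs, nasal ulceration, abscess or necrosis, and acute weakness; a non-serious Grade 3 laboratory value is not among them.

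**Size.** Let q be the share of Visit 2 samples drawn on Day 10 and p the true rate of one related Grade 3 laboratory event. The documents give neither; both are assumed.

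If exactly two cases occur, the rule misses unless both are countable: 1 − (1 − q)². If exactly three occur, it misses when at most one is countable: P(Bin(3, 1 − q) ≤ 1).

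| Cases | q = 5% | q = 10% | q = 20% |
|---|---|---|---|
| Two | 9.75% | 19% | 36% |
| Three | 0.7% | 2.8% | 10.4% |

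Those figures are conditional on the cases occurring. The unconditional chance that the rule fires among the 15 + 15 + 5 = 35 BPZE1 recipients is P(X ≥ 2), with X ~ Bin(35, p(1 − q)):

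| p | q = 0 | q = 5% | q = 10% | q = 20% |
|---|---|---|---|---|
| 0.5% | 1.3% | 1.2% | 1.1% | 0.9% |
| 1% | 4.8% | 4.4% | 4.0% | 3.2% |
| 2% | 15.5% | 14.3% | 13.1% | 10.8% |
| 5% | 52.8% | 50.0% | 47.1% | 41.1% |
| 10% | 87.8% | 85.8% | 83.6% | 78.2% |

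The largest loss shown is 52.8 − 41.1 = 11.7 points.

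**The case against.** The strongest reply concerns weight. The gap is one day at the edge of a window, and the nominal Day 8 sample counts. It matters only if the events are the same term, Grade 3, related, non-serious, and so few that dropping the Day 10 samples leaves fewer than two. The Appendix B Grade 3 limits are extreme for screened healthy adults, and nothing in the Phase 1 summaries suggests rates of 5% to 10% for one laboratory term, though those summaries do not report laboratory rates. This stands: at p of 0.5% to 1% the loss is only 0.1 to 1.6 points.

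Other safeguards also remain. One related SAE halts the trial, and an important medical event can qualify as an SAE. DMID may suspend at any time, and its authority is not limited to the halting criteria. The SMC can be convened ad hoc, and the independent safety monitor may review other adverse events as needed. A Day 10 value is still recorded, graded and followed. But these routes are either discretionary or require seriousness, which a Grade 3 value alone does not establish. None makes the value count toward the stated criterion.

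Finally, the rule refers to when a subject experiences the event, not when blood is drawn, so a Day 10 value with documented earlier onset could count. That would need an unscheduled or outside test, because no earlier post-vaccination sample is scheduled.

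**Conclusion.** The concern holds. On the documents' own numbering, an on-time Day 10 safety sample falls one day beyond the laboratory halting criterion, and no other text brings it back. The mismatch depends only on the wording; its size depends on the assumed q and p. Across the values shown, the loss in the chance of an automatic halt runs from 0.1 points to about 12 points, with the upper end requiring p = 5% and one Visit 2 in five on Day 10. The gap is confined to the automatic laboratory trigger. It is narrow, but worth closing because the remedy costs almost nothing.

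**What to change.** In Protocol 9.5, for the laboratory criterion only, change the limit to 9 days after vaccination (through Day 10). An alternative wording with the same effect for on-time visits is: *within 8 days after vaccination, or at the Visit 2 (Day 8 ± 2) safety sample if later*. Either keeps everything that counts now, including a repeat taken by Day 9, and adds the Day 10 sample. The other criteria in that list can stay at 8 days. Whether repeats at Visit 3 should also count is the sponsor's choice.

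The cost is one number or one clause, with no added visits, blood or analyses. The downside is a slightly higher chance of an unneeded pause for SMC review. For example, assume a 0.5% background rate of such events judged related across all 50 subjects, and q = 10%. Then P(X ≥ 2) rises from 2.2% under Bin(50, 0.0045) to 2.6% under Bin(50, 0.005).
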